1.2 Version History

- The document was initially developed as Version 1.0, based on Protocol Version 1.0, dated October 11, 2019.
- No changes were made after review of Protocol Version 1.0, Letter of Amendment #1, dated January 28, 2020.
- The document was revised after review of Protocol Version 2.0 (dated July 1, 2020) due to the changes in secondary objective: Group A Secondary Objective 7 and Group B Secondary Objective 4. At the time of this review, subset analyses were added as Report Content 11.
- No changes were made based on the review of Protocol Version 2.0, Letter of Amendment #1 (dated February 18, 2022 and released on April 21, 2022). At the time of this review, the document was revised to incorporate ICH E9(R1) recommendations.
 - A new section on estimands (Section 4) was added. Subsequent section numbers were updated. Section 5 heading was renamed to better describe its contents.
 - Items related to analysis sets, outcome measures and handling of missing data were moved to Section 4 and edited for clarification. Additional missing data considerations

were added for sensitivity analyses, given the potential for more missing data than anticipated due to the COVID-19 pandemic.

- A summary about intercurrent events was added in Section 6. Minor edits were made in Section 6 for clarification and readability. Additional details about the statistical analyses with references were added in Sections 4 and 5.
- No changes were made based on the review of Protocol Version 3.0 (dated December 13, 2022).

2 Study Overview

2.1 Study Design

A5379 is a prospective, open-label study to evaluate immunogenicity of the HBV vaccine HEPLISAV-B in two study populations living with HIV: prior HBV vaccine recipients who are deemed non-responders (Group A) and individuals who are naïve to HBV vaccination (Group B). The study is designed separately for the two study populations and will be conducted as separate evaluations for all primary and key secondary analyses. No adjustment of type I error is planned for conducting two population studies under the same protocol mainly for administrative efficiency.

2.1.1 Group A (Non-responders, N=561)

The study is designed as an open-label three-arm study, where participants are randomized in 1:1:1 ratio to the following study arms, stratified by sex at birth (male vs. female) and diabetes diagnosis status (yes vs. no).

- Arm 1: Two doses of HEPLISAV-B at weeks 0 and 4
- Arm 2: Three doses of HEPLISAV-B at weeks 0, 4, and 24
- Arm 3: Three doses of ENGERIX-B at weeks 0, 4, and 24

Randomization will use permuted blocks and balancing by main site.

2.1.2 Group B (Vaccine-Naïve, N=73)

Group B study is designed as a single-arm study.

2.2 Hypotheses

2.2.1 Group A

- In participants living with HIV, HEPLISAV-B vaccination given as a two-dose series achieves non-inferior seroprotection response (SPR) proportion compared to standard dose ENGERIX-B.
- 2. In participants living with HIV, HEPLISAV-B vaccination given as a three-dose series achieves superior SPR proportion compared to standard dose ENGERIX-B.
- 3. HEPLISAV-B vaccination given as a two-dose series or a three-dose series is safe in participants living with HIV.

2.2.2 Group B

- 1. In participants living with HIV, HEPLISAV-B vaccination given as a three-dose series achieves SPR proportion greater than 55%.
- 2. HEPLISAV-B vaccination given as a three-dose series is safe in participants living with HIV.

2.3 Study Objectives

This Primary SAP addresses the following primary and secondary objectives in the study protocol. Other study objectives in the protocol will be addressed in subsequent analysis plans.

2.3.1 Primary Objectives

The comparison of SPR between Arms 1 and 3 will be conducted as non-inferiority. Such comparison between Arms 2 and 3 will be conducted as superiority.

Group A

- To compare the week 12 SPR of a two-dose regimen of HEPLISAV-B (Arm 1) versus the week 28 SPR of a standard three-dose regimen of ENGERIX-B (Arm 3) in hepatitis B virus (HBV) vaccine-experienced participants living with HIV.
- 2. To compare the week 28 SPR of a three-dose regimen of HEPLISAV-B (Arm 2) versus a standard three-dose regimen of ENGERIX-B (Arm 3) in HBV vaccine-experienced participants living with HIV.
- 3. To describe adverse events (AEs) reported in each study arm over the duration of the study.

Group B

- 1. To determine the week 28 SPR of a three-dose regimen of HEPLISAV-B in HBV vaccinenaïve participants living with HIV.
- 2. To describe AEs reported over the duration of the study.

2.3.2 Secondary Objectives

Group A

- 1. To compare the week 12 geometric mean titers (GMT) of a two-dose regimen of HEPLISAV-B (Arm 1) versus the week 28 GMT of a standard three-dose regimen of ENGERIX-B (Arm 3) in HBV vaccine-experienced participants living with HIV.
- To compare the week 28 GMT of a three-dose regimen of HEPLISAV-B (Arm 2) versus a standard three-dose regimen of ENGERIX-B (Arm 3) in HBV vaccine-experienced participants living with HIV.
- 3. To compare the SPR and GMT 4, 8, 24, and 48 weeks after last vaccination of a two-dose regimen of HEPLISAV-B (Arm 1) versus a standard three-dose regimen of ENGERIX-B (Arm 3) in HBV vaccine-experienced participants living with HIV.

- 4. To compare the SPR and GMT 8, 24, and 48 weeks after last vaccination of a three-dose regimen of HEPLISAV-B (Arm 2) versus a standard three-dose regimen of ENGERIX-B (Arm 3) in HBV vaccine-experienced participants living with HIV.
- 5. To compare the SPR and GMT 4, 8, 24 and 48 weeks after last vaccination of a two-dose regimen of HEPLISAV-B (Arm 1) versus a three-dose regimen of HEPLISAV-B (Arm 2) in HBV vaccine-experienced participants living with HIV.
- 6. To assess SPR and GMT at weeks 4, 8, 12, and 24 between HEPLISAV-B (Arms 1 and 2 combined) and ENGERIX-B (Arm 3) in HBV vaccine-experienced participants living with HIV (Group A).
- To describe incidence of Grade≥2 AEs within 4 weeks of each injection in each study arm.
- 8. To assess host characteristics associated with vaccine response.
- 9. To compare SPR and GMT at week 72 between HEPLISAV-B two-dose (Arm 1) and three-dose arms (Arm 2).

Group B

- 1. To determine the week 28 GMT of a three-dose regimen of HEPLISAV-B in HBV vaccine-naïve participants living with HIV.
- 2. To determine the SPR and GMT of a three-dose regimen of HEPLISAV-B at weeks 32, 48, and 72 in HBV vaccine-naïve participants living with HIV.
- 3. To determine the SPR and GMT of a three-dose regimen of HEPLISAV-B at weeks 4, 8, 12, and 24 in HBV vaccine-naïve participants living with HIV.
- 4. To describe incidence of Grade ≥2 AEs within 4 weeks of each injection.
- 5. To assess host characteristics associated with vaccine response.

2.4 Overview of Sample Size Considerations

2.4.1 Group A

A two-sided type I error rate is targeted at the pre-specified overall alpha level of 5% for the two primary analysis comparisons in Group A. To preserve the overall type I error rate in Group A and to allow flexible interim monitoring, a Bonferroni correction is applied, and a two-sided type I error rate of 2.5% each for the non-inferiority comparison between Arm 1 and Arm 3 and for the superiority comparison between Arm 2 and Arm 3 is allocated.

The sample size of N=187 per arm was derived as follows.

1. Non-inferiority comparison between Arms 1 and 3: For the primary objective to show that SPR proportion in Arm 1 is non-inferior to the SPR proportion in Arm 3 within the non-inferiority margin of 10%, we assume that 70% in the control arm (Arm 3) will achieve SPR. We assume the proportion of participants achieving SPR with two doses of HEPLISAV-B (Arm 1) will be higher at 75%. As a non-inferiority design, this comparison is powered to show that the SPR proportion in Arm 1 is not lower than that of Arm 3 (control) by more than the pre-specified non-inferiority margin of 10%. A sample size of 168 each in Arm 1 and Arm 3 achieves 80% power to detect a difference between the two proportions of less than 10%, in a one-sided test with type I error of 1.25% using

Page 7 of 25

normal approximation. Assuming no more than about 10% missing data for SPR, which includes loss to follow-up within each study arm prior to the primary outcome visit, the sample size is increased to 187 per study arm.

2. Superiority comparison between Arms 2 and 3: For the primary objective to compare SPR proportions between Arm 2 and Arm 3 (control), an increase of 15% is assumed in the proportion of participants achieving SPR with three doses of HEPLISAV-B (Arm 2). With the sample size of 147 participants in each study arm, there is 80% power to detect a difference as significant in a two-sided test at a significance level of 2.5% using normal approximation. Formal interim efficacy analyses are planned for the Arm 2 and Arm 3 comparison, should the study enrollment allow such interim analyses to be useful to affect the conduct of the study. Assuming no more than three interim analyses for the study and applying the O'Brien and Fleming approach to preserve the two-sided type I error rate at 2.5%, Arm 2 and Arm 3 sample sizes should be at least 149 per study arm. Assuming no more than about 10% loss in the SPR data within each study arm, the targeted study sample size is 166 each for Arm 2 and Arm 3 to retain 80% power. To maintain 1:1:1 randomization across Arms 1, 2, and 3 throughout enrollment, the sample size in Arm 2 is increased to 187. Therefore, the power for the comparison between Arm 2 and Arm 3 is higher than 80%.

2.4.2 **Group B**

The study is powered to conclude that the proportion achieving SPR is greater than 55%. Assuming a response proportion of 75%, a sample size of 65 would provide at least 90% power in a two-sided test using normal approximation at a targeted significance level of 5%. Assuming at most 10% missing data, including loss to follow-up prior to the primary outcome visit, the study sample size is increased to 73.

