2.5.1 Group A

Interim monitoring is considered independently for the two primary objectives as follows.

- 1. Non-inferiority comparison between Arms 1 and 3:
 - a. For the primary objective on the comparison between Arm 1 and Arm 3, interim monitoring will not include early formal non-inferiority analyses using the accumulating data on the primary outcome for early study conclusion on noninferiority. This is because the long-term antibody data in the study provide important supporting information on how the primary results in these study arms should be interpreted for future guidance.
 - b. Early stopping due to concerns on poor vaccine responses in Arm 1 beyond the non-inferiority margin of 10% in SPR compared to Arm 3 (control arm) that may be

deemed harmful may occur. For this purpose, the SPR estimates for the primary outcome measure will be provided with a two-sided 99.9% confidence interval around the difference in the proportion estimates (Arm 3 minus Arm 1). As a guideline, a lower bound of the confidence interval above 10% may be considered evidence towards poor response in Arm 1 that suggests potential harm.

2. Superiority comparison between Arms 2 and 3:

- a. Formal efficacy interim analyses are planned for the second primary objective on the comparison between Arm 2 and Arm 3 (control arm), should the study enrollment allow such interim analyses to be useful to affect the conduct of the study. The initial interim efficacy analysis on the primary outcome for this comparison is aimed at when at least 40% of the SPR results at 4 weeks after the vaccination series are available for analysis. The Lan-DeMets spending function for type I error (alpha) with O'Brien-Fleming type boundaries will be employed. With this approach, two-sided type I error rate for efficacy at the 0.025 level will be preserved regardless of the number and timing of the analysis. If the confidence interval at the interim look lies entirely above zero and the interim data review identifies no concerns, early stopping of Arm 2 to conclude Arm 2 superiority may occur.

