5.2 Analysis Approaches

5.2.1 Group A Primary:

- For each of the two primary objectives on vaccine response, the primary outcome measure on the SPR will be analyzed as a binary variable.
- A score-based approach similar to the Wilson method for a SPR proportion difference will be used to estimate a stratified confidence interval, known as Newcombe method (Yan

- and Su, 2010). Four strata will be defined by sex at birth and screening diabetes status, and the strata will use Mantel-Haenszel weights (Mantel and Haenszel. 1959).
- Non-inferiority comparison between Arms 1 and 3: For the final analysis, a two-sided 97.5% confidence interval will be provided for the estimated proportion difference between Arm 1 and Arm 3 (Arm 3 minus Arm 1). If the resulting confidence interval lies entirely below the non-inferiority margin of 10%, then non-inferiority of Arm 1 compared to Arm 3 (control) will be concluded. Superiority of Arm 1 compared to Arm 3 will be concluded if the confidence interval lies entirely below zero.
- Superiority comparison between Arms 2 and 3: For the final analysis, a two-sided 97.5% stratified confidence interval will be provided for the proportion difference between Arm 2 and Arm 3 (Arm 2 minus Arm 3). A repeated confidence interval approach according to the realized Lan and DeMets implementation of the O'Brien-Fleming sequential stopping boundary that accounts for the repeated analyses due to interim efficacy monitoring will be provided. If the resulting confidence interval lies entirely above zero, then superiority of Arm 2 compared to Arm 3 (control) will be concluded.
- To address the study objectives on safety, the proportion of participants with AEs will be summarized with a two-sided 95% confidence interval in each study arm using the Wilson method, across stratification factors.

5.2.2 Group A Secondary:

- The secondary analyses on SPR will be conducted using a two-sided type I error rate of 2.5% without further correction for multiple analyses. This type I error was chosen to provide confidence intervals of widths comparable to the primary outcome analyses.
- The secondary objectives on the SPR comparisons will be addressed using the following analysis approach. A two-sided 97.5% confidence interval around the difference in proportions will be calculated using the Newcombe method. These will also be stratified confidence intervals, similar to the primary analysis approach.

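### A cheap improvement, not an error: passing the 2.5% of a successful Arm 2 superiority test to the Arm 1 non-inferiority test would add about 5 points of power at the SAP's assumptions

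*SAP*

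**What the plan says.** SAP 2.4.1 sets the family-wise target: "A two-sided type I error rate is targeted at the pre-specified overall alpha level of 5% for the two primary analysis comparisons in Group A". It then divides that total: "a Bonferroni correction is applied, and a two-sided type I error rate of 2.5% each", one share for the Arm 1 versus Arm 3 non-inferiority comparison and one for the Arm 2 versus Arm 3 superiority comparison. The reasons given are control of the overall error and flexibility for interim monitoring.

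Only the superiority comparison has efficacy looks. SAP 2.5.1 gives it a Lan-DeMets spending function with O'Brien-Fleming type boundaries at two-sided 0.025. For Arm 1 versus Arm 3 the same section says that "interim monitoring will not include early formal non-inferiority analyses". What remains for that pair is a harm guideline based on a 99.9% interval, for which SAP 5.1 makes no alpha adjustment.

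SAP 5.2.1 fixes the final non-inferiority rule: "For the final analysis, a two-sided 97.5% confidence interval will be provided for the estimated proportion difference between Arm 1 and Arm 3". The level is the same whatever Arm 2 shows. The same interval also serves a nested conclusion that Arm 1 is superior to Arm 3. No section of the SAP reallocates alpha from a successful comparison to the other one.

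**The concern.** The non-inferiority comparison sets the trial's size: it needs 168 evaluable per arm, against 149 for superiority with interim looks. It is powered at 80%. If Arm 2 succeeds, the superiority share of the error has served its purpose, and a closed test may use it again. Under the current rule it lapses.

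Interim flexibility is a good reason not to let alpha flow into the superiority test, because that would change its final boundary. It does not bear on the opposite direction. Non-inferiority is tested once, at the end, so it can receive alpha without touching any boundary, look time or repeated confidence interval. At stake is some power for the Arm 1 claim, and for making both claims, with no more participants.

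**Working it through.** **Inputs.** From SAP 2.4.1: "within the non-inferiority margin of 10%, we assume that 70% in the control arm (Arm 3) will achieve SPR"; SPR with "two doses of HEPLISAV-B (Arm 1) will be higher at 75"%; Arm 2 at 70% + 15 points = 85%; the non-inferiority sample size was found "in a one-sided test with type I error of 1.25% using" a normal approximation. Arm 3 is shared by both comparisons.

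**The SAP's own figures.**
- Non-inferiority: n = (2.2414 + 0.8416)² × (0.70×0.30 + 0.75×0.25) / (0.10 + 0.05)² = 9.505 × 0.3975 / 0.0225 = 167.9, so 168. Then 168/0.9 = 186.7, so 187.
- Superiority, pooled variance with mean proportion 0.775: n = [2.2414 × √(2×0.775×0.225) + 0.8416 × √(0.21 + 0.1275)]² / 0.15² = 146.0, stated as 147. With interim looks, 149/0.9 = 165.6, so 166.

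All four stated figures reproduce.

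**Power at 168 evaluable per arm (normal approximation).**
1. Standard error for Arm 1 versus Arm 3: √(0.3975/168) = 0.0486. The standardised distance from the margin is 0.15/0.0486 = 3.084.
2. Non-inferiority power at one-sided 1.25%: Φ(3.084 − 2.241) = 80.0%. At one-sided 2.5%: Φ(3.084 − 1.960) = 86.9%.
3. Superiority power: 85.7%.
4. Correlation through the shared control: 0.21/√(0.3975 × 0.3375) = 0.573.
5. Under one-way passing, non-inferiority is concluded if the 97.5% interval succeeds, or if superiority and the 95% interval both succeed. So power = P(NI at 1.25%) + P(NI at 2.5% and superiority) − P(NI at 1.25% and superiority) = 80.0% + 78.4% − 73.3% = 85.1%, a gain of 5.1 points.

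The joint terms also show that power to make both claims rises from 73.3% to 78.4%. If all 187 per arm are evaluable, non-inferiority power goes from 84.4% to 88.9%.

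**Simulation check.** Unstratified Newcombe intervals give 80.6% to 85.7%. With interim looks at 40, 60, 80 and 100% the result is 80.5% to 85.5%. Those look times are an assumption: the SAP gives only a first look at 40% or more and at most three interims.

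**Dependence on Arm 2** (Arm 1 75%, Arm 3 70%, 168 per arm):

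| Arm 2 SPR | Gain, normal approximation | Gain, Newcombe simulation |
|---|---|---|
| 85% | +5.1 | +5.1 |
| 82% | +2.8 | +3.0 |
| 80% | +1.5 | +1.7 |
| 75% | +0.1 | +0.2 |

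If Arm 1 is only equal to Arm 3 at 70%, with Arm 2 at 85%, non-inferiority power goes from 40.5% to 50.6% (normal approximation).

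**Error control, one-sided against 2.5%.**
- Both nulls true (Arm 1 60%, Arm 2 70%, Arm 3 70%): the chance of any false claim is 2.4% under either rule. A false non-inferiority claim at the wider level needs a superiority rejection that already counts as an error.
- Only the non-inferiority null true (Arm 1 60%, Arm 2 85%): the false-claim rate is 1.3% under the current rule. With passing it is 2.5% with Wald intervals and 2.6% with Newcombe. The excess over 2.5% belongs to the Newcombe interval, whose plain 1.25% test already runs at 1.34%.

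**The case against.** The strongest reply is that nothing is broken. Bonferroni is valid, was pre-specified with a reason, and delivers the 80% power the design asked for. A reader might infer that the split is a mistake or that the trial is underpowered. The documents do not support that: every stated sample size reproduces, and with all 187 per arm evaluable non-inferiority power is already 84.4%. This part stands in full.

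Second, the power is not free. It comes from a looser criterion for Arm 1. The family-wise limit is unchanged, but the false non-inferiority rate at the margin roughly doubles when Arm 2 is truly superior. This stands and must be stated beside the gain.

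Third, a reader might take 5 points as unconditional. It is not: it rests on Arm 2 reaching about 85%.

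Fourth, a reader might infer that the sponsor weighed alpha passing and rejected it because of monitoring. The SAP does not discuss it. SAP 2.5.1 does treat interim monitoring of the two objectives as independent. One-way passing leaves the monitoring so, but the two final decisions would no longer be independent.

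Fifth, other parts of the SAP lean on the fixed level. Section 5.2.2 picks 97.5% for secondary SPR intervals so that their widths match the primary ones, and the supplementary analyses in Section 6 item 13 refer back to 5.2.1. The trigger (crossing the boundary or stopping Arm 2) and the level for the nested Arm 1 superiority conclusion must also be settled. These are drafting gaps that a few sentences can close.

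Last, loosening a primary criterion late in an open-label trial under DSMB review invites challenge. This stands as a condition on timing.

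**Conclusion.** The point holds as a cheap improvement to a valid plan. One-way passing of alpha is a closed test. It keeps the 5% two-sided family-wise limit, leaves the superiority boundaries alone, and cannot lower non-inferiority power, because a failed superiority test leaves the 97.5% interval in force.

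At 75%, 85% and 70% with 168 evaluable per arm the gain is about 5 points (80% to 85%). To reach 85.1% under the current rule would take about (2.2414 + 1.041)² × 0.3975/0.0225 ≈ 190 evaluable per arm. The gain shrinks to about 3 points with Arm 2 at 82%, 1.7 at 80%, and near zero at 75%.

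Against this, the nominal one-sided false-claim rate at the margin goes from 1.25% to 2.5% when Arm 2 is truly superior (about 1.3% to 2.6% simulated), which uses the family-wise limit fully.

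The figures assume equal evaluable numbers per arm and unstratified intervals. The SAP's stratified interval could not be simulated exactly because stratum sizes are not given.

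**What to change.** By a pre-specified amendment, made before anyone deciding on it has seen comparative data, state in SAP 2.4.1 and 5.2.1 that:

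- Arm 2 versus Arm 3 superiority is tested at two-sided 2.5% with its Lan-DeMets O'Brien-Fleming boundary, unchanged.
- If that boundary is crossed at an interim or the final analysis, whether or not Arm 2 is stopped, the Arm 1 versus Arm 3 decision uses a two-sided 95% interval; otherwise it uses 97.5%. The same interval governs the nested Arm 1 superiority conclusion.
- Both the 95% and the 97.5% intervals for Arm 1 versus Arm 3 are reported.
- Secondary SPR intervals in 5.2.2 and the supplementary analyses in Section 6 item 13 stay at 97.5%.

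The cost is wording, with no added participants and no change to monitoring. The protocol text available here is the letter of amendment. If the protocol's statistical section repeats the fixed split, it needs the same change. The lasting downsides are that the Arm 1 decision level depends on the Arm 2 result, and the higher false-claim rate at the margin described above. If comparative data have already reached those who would decide, the current rule should stand.

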2.5 Overview of Formal Interim Monitoring

The study will be monitored by an independent DAIDS-appointed Data and Safety Monitoring Board (DSMB). The initial interim data review by the DSMB will occur no later than one year after the enrollment of the first participant in the study in either Group A or B.

2.5.1 Group A

Interim monitoring is considered independently for the two primary objectives as follows.

- 1. Non-inferiority comparison between Arms 1 and 3:
 - a. For the primary objective on the comparison between Arm 1 and Arm 3, interim monitoring will not include early formal non-inferiority analyses using the accumulating data on the primary outcome for early study conclusion on noninferiority. This is because the long-term antibody data in the study provide important supporting information on how the primary results in these study arms should be interpreted for future guidance.
 - b. Early stopping due to concerns on poor vaccine responses in Arm 1 beyond the non-inferiority margin of 10% in SPR compared to Arm 3 (control arm) that may be

deemed harmful may occur. For this purpose, the SPR estimates for the primary outcome measure will be provided with a two-sided 99.9% confidence interval around the difference in the proportion estimates (Arm 3 minus Arm 1). As a guideline, a lower bound of the confidence interval above 10% may be considered evidence towards poor response in Arm 1 that suggests potential harm.

2. Superiority comparison between Arms 2 and 3:

- a. Formal efficacy interim analyses are planned for the second primary objective on the comparison between Arm 2 and Arm 3 (control arm), should the study enrollment allow such interim analyses to be useful to affect the conduct of the study. The initial interim efficacy analysis on the primary outcome for this comparison is aimed at when at least 40% of the SPR results at 4 weeks after the vaccination series are available for analysis. The Lan-DeMets spending function for type I error (alpha) with O'Brien-Fleming type boundaries will be employed. With this approach, two-sided type I error rate for efficacy at the 0.025 level will be preserved regardless of the number and timing of the analysis. If the confidence interval at the interim look lies entirely above zero and the interim data review identifies no concerns, early stopping of Arm 2 to conclude Arm 2 superiority may occur.
- b. Early stopping due to concerns about poor vaccine responses in Arm 2 compared to Arm 3 (control arm) may occur. For this purpose, the SPR estimates for the primary outcome measure will be provided with a two-sided 99.9% confidence interval around the difference in the proportion estimates (Arm 3 minus Arm 2), similar to the Arm 3 comparison to Arm 1 discussed above in assessing potential harm. As a guideline, a lower bound of the confidence interval above 10% may be considered as evidence towards poor response in Arm 2 that suggests potential harm.

